### **11.5 – Tertiary Endpoint #5**

Endpoint Description: Time to cardiovascular death or first unplanned heart failure hospitalization through 24 weeks, using the pre-COVID-19 population.

Response Variable Definition: Site-classified cardiovascular death or unplanned heart failure hospitalizations occurring from the time of randomization through the Week 24 assessment. The event time will be set at the time of the earliest of cardiovascular death or first unplanned heart failure hospitalization. In the event the patient did not have complete follow-up through Week 24, the patient will be censored at the time of their last follow-up prior to the Week 24 assessment.

Additional Covariates in Addition to Randomized Treatment: atrial fibrillation status at time of randomization

Handling of Dropouts and Missing Data: Each patient will be evaluated based on the available follow-up. No adjustment for incomplete follow-up will be made.

Sensitivity Analysis: Re-calculate the endpoint analysis using the original ITT population.

Statistical Tests: The Cox regression model for survival data (PROC PHREG in SAS) will be used to test the statistical significance of differences in time to cardiovascular death or first unplanned heart failure hospitalization between the treatments. Kaplan-Meier curves will be generated to graphically display the event rates as a function of time from randomization in each treatment.

Interpretation of Results: A lower rate of unplanned heart failure hospitalizations or cardiovascular death through 24 weeks indicates lower clinical event rates in the LCZ696 arm versus Valsartan.

## 11.6 – Tertiary Endpoint #6

Endpoint Description: Total number of unplanned heart failure hospital admissions through 24 weeks, using the pre-COVID-19 population.

Response Variable Definition: Number of unplanned heart failure hospitalizations between Randomization and Week 24.

Additional Covariates in Addition to Randomized Treatment: atrial fibrillation status at time of randomization

Handling of Dropouts and Missing Data: Each patient will be evaluated based on the available follow-up. No adjustment for incomplete follow-up will be made.

Sensitivity Analysis: Re-calculate the endpoint analysis using the original ITT population.

Statistical Tests: A Poisson regression model (PROC GENMOD in SAS) will be used to estimate and statistically compare whether there is differential rate of subjects experiencing unplanned heart failure hospital admissions between the treatments.

Interpretation of Results: A smaller number of unplanned heart failure hospitalizations through 24 weeks indicates a reduction in admissions in the LCZ696 arm versus Valsartan.

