9 PATIENT POPULATION

9.1 Study Population

It is anticipated that approximately 400 subjects meeting eligibility criteria listed below will be randomized into the study. Subjects suitable for this protocol are individuals with advanced HF and a LVEF \leq 35%. Subjects may be currently hospitalized or non-hospitalized.

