9.2 Inclusion Criteria

Key inclusion criteria

1. Advanced HF \geq EF defined as including ALL
 - a. LVEF \leq 35% documented during the preceding 12 months
 - b. NYHA class IV symptomatology, defined as chronic dyspnea or fatigue at rest or on minimal exertion in the previous 3 months, or patients who require chronic inotropic therapy
 - c. Minimum of 3 months GDMT for HF and/or intolerant to therapy
2. Systolic blood pressure \geq 90 mmHg
3. Serum NT-proBNP \geq 800 pg/mL OR BNP \geq 250 pg/mL (most recent - less than 3 months old)
4. Any one or more of the following objective findings of advanced HF including:

- a. Current inotropic therapy or use of inotropes in the past 6 months
 - b. ≥ 1 hospitalization for heart failure in the past 6 months (not including the index hospitalization for inpatient participants)
 - c. LVEF $\leq 25\%$ (within the past 12 months)
 - d. Peak VO₂ $< 55\%$ predicted or peak VO₂ ≤ 16 for men or ≤ 14 for women (Respiratory Exchange Ratio (RER) ≥ 1.05) (within the past 12 months)
 - e. 6 min walk test distance < 300 m (within the past 3 months)
5. Age ≥ 18 years and ≤ 85 years
 6. Signed Informed Consent form

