#### 4. General Methodology

Medians, 25th and 75th percentiles will be presented for continuous variables; the number and percentage of patients in each category will be presented for categorical variables. For all endpoints a p-value  $\leq 0.05$  will be considered statistically significant and all tests will be 2-sided. Analyses will be performed using validated SAS software (SAS Institute, Inc., Cary, NC). Appropriate statistical models will be used to examine the effect of treatment on both the primary, secondary, and tertiary outcomes in the study.

The modeling that will be used for each endpoint will be detailed within each endpoint description section.

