## 12. Exploratory Endpoint Descriptions

### 12.1 – Exploratory Endpoint #1

Endpoint Description: A four level modified clinical composite endpoint including 1) death, 2) LVAD or Heart Transplant (including listing status of 1A, 1B or 1-4), 3) multiple HF hospital admissions, and 4) single HF admission, using the pre-COVID-19 population.

Response Variable Definition: The unmatched approach to the win ratio of Pocock will be used. In general terms, each patient will be placed into one of the hierarchical groups based on the comparison of LCZ696 versus Valsartan patients. The hierarchy for the comparisons is as follows:

- (a) LCZ696 patient had death first
- (b) Valsartan patient had death first
- (c) LCZ696 patient had LVAD or HTP first
- (d) Valsartan patient had LVAD or HTP first
- (e) LCZ696 patient had multiple HF hospital admissions first
- (f) Valsartan patient had multiple HF hospital admissions first
- (g) LCZ696 patient had single HF hospital admission first
- (h) Valsartan patient had single HF hospital admission first
- (i) None of the above

Additional Covariates in Addition to Randomized Treatment: None

Handling of Dropouts and Missing Data: All patients are expected to have some data to address this endpoint. No further adjustments for incomplete or missing data will be made.

Sensitivity Analysis: Re-calculate the endpoint analysis using the original ITT population.

Statistical Tests: The win ratio approach of Pocock will be used to evaluate each endpoint. Calculation of the test statistics, p-values and confidence intervals is detailed in the Pocock manuscript (Pocock SJ, Ariti CA, Collier TJ, Wang D. The win ratio: A new approach to the analysis of composite endpoints in clinical trials based on clinical priorities. *Eur Heart J*.33:176-182).

Interpretation of Results: A win ratio of 1.0 is the null value. Estimates below 1.0 indicate a worse outcome and win ratios greater than 1.0 indicate a favorable effect for the LCZ696 arm.

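### SAP 11.6 tests repeat HF admission counts by plain Poisson regression; if admission risk varies between patients beyond AF status, the standard error is too small and the test exceeds 5%

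*SAP*

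**What the plan says.** SAP 11.6 defines the response as a count per patient: "Number of unplanned heart failure hospitalizations between Randomization and Week 24". The test sentence reads "A Poisson regression model (PROC GENMOD in SAS) will be used to estimate and statistically compare", and it describes the quantity compared as a "differential rate of subjects experiencing unplanned heart failure hospital admissions between the treatments". AF status at randomization is the only covariate besides treatment. For incomplete data it says: "Each patient will be evaluated based on the available follow-up. No adjustment for incomplete follow-up will be made". The single sensitivity analysis repeats the model in the original ITT population.

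No other section supplies a variance method. SAP 4 leaves modelling detail to the endpoint sections and applies the 0.05 threshold to every endpoint, where a result at or below it "will be considered statistically significant and all tests will be 2-sided". Protocol 16.5 names general linear, mixed, Cox and win-ratio methods but nothing for counts. Protocol 16.1 requires all planned analyses to be defined before unblinding.

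On the population, Protocol 9.1 states: "Subjects may be currently hospitalized or non-hospitalized". Protocol 9.2 requires "Any one or more of the following objective findings of advanced HF including" five alternatives, of which a recent HF hospitalization is one.

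**The concern.** The Poisson standard error is right only if, given treatment and AF status, patients share one admission rate. When rates differ between patients, the variance of the counts exceeds their mean and the model-based standard error is too small.

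The entry criteria make differing rates plausible. An inpatient with a recent HF admission and an outpatient who qualifies on ejection fraction or walk distance can both enter, and AF status does not separate them.

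At stake are the p-value and confidence interval for total HF admissions: a difference could be declared at 0.05 more often than the plan intends. The planned sensitivity analysis cannot show this, because it changes the patients and keeps the variance assumption.

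**Working it through.** **Inputs from the documents.** 335 patients in the pre-COVID-19 population and 365 in the ITT sensitivity analysis (SAP 3); 1:1 allocation (SAP 2.2); two-sided 0.05 (SAP 4). The nearest event figure is 40% at 24 weeks in the valsartan arm for death or first HF re-admission (Protocol 16.2).

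**Assumed, because the documents do not give them.** Mean admissions per patient μ from 0.3 to 0.7, and heterogeneity k from 0.5 to 2. As a guide to the mean, a 40% event share under a homogeneous Poisson corresponds to −ln(0.60) = 0.51. That is an upper guide, since the 40% includes deaths.

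**Formula.** Let φ = variance/mean. The Wald test from an unscaled Poisson model has true size 2 × [1 − Φ(1.96/√φ)], and its standard error is too small by the factor 1/√φ.

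**Step 1: reproduce the nominal level.** φ = 1 gives 5.0%. Simulation at 335 patients, mean 0.5 and no heterogeneity gave 4.96% (10,000 runs).

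**Step 2: one identifiable risk group.** φ = 1 + Var(rate)/μ.
- Mean 0.3, half the patients at a 2-fold rate: rates 0.2 and 0.4, variance 0.01, φ = 1.033, size 5.4%.
- Mean 0.5, 30% of patients at a 3-fold rate: rates 0.3125 and 0.9375, variance 0.3 × 0.7 × 0.625² = 0.082, φ = 1.164, size 6.9%.
- Mean 0.7, 30% at a 3-fold rate: rates 0.4375 and 1.3125, variance 0.3 × 0.7 × 0.875² = 0.161, φ = 1.230, size 7.7%.

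Simulated sizes were 5.1%, 6.8% and 7.9%.

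**Step 3: gamma-distributed risk (negative binomial counts).** φ = 1 + kμ. The share of patients with an admission is 1 − (1 + kμ)^(−1/k). Simulated values use 20,000 trials of 167 against 168 patients with no true effect.

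| μ, k | φ | Share with an admission | Size, formula | Size, simulated | Simulated, at most 3 admissions |
|---|---|---|---|---|---|
| 0.3, 0.5 | 1.15 | 24% | 6.8% | 6.8% | 6.0% |
| 0.5, 1 | 1.50 | 33% | 11.0% | 10.9% | 8.2% |
| 0.7, 2 | 2.40 | 35% | 20.6% | 20.4% | 11.0% |

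Over the whole grid the share with an admission runs from 1 − 1.6^(−1/2) = 21% (μ 0.3, k 2) to 1 − 1.35^(−2) = 45% (μ 0.7, k 0.5). The top of that range lies above the protocol's 40%, so part of the grid is outside that guide.

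**Step 4: does the AF covariate help?** With treatment and AF in the model and 335 patients, simulated size was 5.1% with no heterogeneity and 11.4% at mean 0.5, k 1. Adjusting for AF does not remove variation unrelated to AF.

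**Step 5: robust variance.** In the runs without a covariate, robust size over the overdispersed settings was 4.8% to 5.9% at 335 and 365 patients. Smaller runs with AF in the model (1,500 to 2,000 trials, Monte Carlo error about 0.5 points) ranged from 4.0% to 6.6%. The level is therefore about 5%, with small-run noise around it.

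**Step 6: effect on the interval.** The mean standard error of the log ratio at mean 0.5, k 1 was 0.156 with Poisson and 0.189 with robust variance; 0.189/0.156 = 1.21, so the interval is 21% wider.

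**The case against.** The strongest reply is that the larger figures have no basis in the documents. That stands. No admission mean or dispersion is given, and everyone enrolled already has class IV symptoms or chronic inotropes, LVEF ≤ 35% and raised natriuretic peptides, which narrows the spread of risk. The settings tied to an identifiable risk group give only about 5% to 8%. The 20% end is an extreme corner, and it falls to 11% if no patient has more than three admissions. It is also fair that this is one of 13 tertiary endpoints, each tested at an unadjusted 0.05, and that HF admissions enter several other endpoints.

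Three stronger readings are tempting and should not be adopted.

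- A reader might infer that the win-ratio tier "LCZ696 patient had multiple HF hospital admissions first", separate from the single-admission tier, shows unequal risk. It does not. A homogeneous Poisson with mean 0.5 gives 1 − e^(−0.5) × 1.5 = 9.0% of patients, about 30 of 335, with two or more admissions.
- A reader might infer that the test sentence makes the outcome yes/no. The same phrasing recurs across the SAP's logistic-regression endpoints, and in 11.6 the title, response and interpretation lines all specify a count.
- A reader might infer that a follow-up offset was overlooked. SAP 11.6 decides against one: "Each patient will be evaluated based on the available follow-up. No adjustment for incomplete follow-up will be made". Unequal follow-up also adds little overdispersion: cutting 20% to 25% of patients short, with no other heterogeneity, gave φ of 1.03 to 1.04 and a size of 4.8% to 5.3%.

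None of this supplies the missing variance method.

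**Conclusion.** The point holds conditionally. SAP 11.6 makes no allowance for overdispersion, and if admission risk varies between patients beyond AF status, the test exceeds its nominal 5%. The documents support the direction of the error and the plausibility of the condition. They do not establish that the counts will be overdispersed, nor by how much.

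Under the assumptions above, the size runs from no inflation, through about 5% to 8% for a single risk group and about 11% at mean 0.5 and k 1, to 7% to 21% over the full grid. The expected rate ratio is unaffected, and so is the primary conclusion. The change is worth making because it is cheap and removes the dependence on an untested assumption.

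**What to change.** In SAP 11.6, keep the count response and the AF covariate. State, before analysis, that the Poisson model is fitted with robust (sandwich) variance by patient, using a REPEATED statement in PROC GENMOD. If the sponsor prefers, name a negative binomial model instead. Robust Poisson leaves the point estimate unchanged. In the trial runs the negative binomial held a similar level (3.9% to 5.2%), but in the non-SAS implementation used it gave no usable standard error in 34 of 1,500 runs at mean 0.3, k 0.5. Apply the same method in the ITT sensitivity analysis.

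As a wording tidy-up only, replace the phrase about the rate of subjects with one that refers to the number of admissions.

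The cost is one or two sentences of SAP text and one line of code, with no new data. The interval widens where counts are overdispersed (about 21% at mean 0.5, k 1) and hardly at all otherwise.

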### **11.7 – Tertiary Endpoint #7**

Endpoint Description: Number of subjects on continuous inotropic therapy  $\geq 7$  days after discharge from the index hospitalization through 24 weeks, using the pre-COVID-19 population.

Response Variable Definition: An indicator for patient taking at least 7 days of continuous inotropic therapy at any time from Randomization (or index hospital discharge if later) through Week 24.

Additional Covariates in Addition to Randomized Treatment: atrial fibrillation status at time of randomization

Handling of Dropouts and Missing Data: Each patient will be evaluated based on the available follow-up. No adjustment for incomplete follow-up will be made.

Sensitivity Analysis: Re-calculate the endpoint analysis using the original ITT population.

Statistical Tests: A logistic regression model (PROC LOGISTIC in SAS) will be used to estimate and statistically compare whether there is differential rate of subjects taking at least 7 days of continuous inotropic therapy between the treatments.

Interpretation of Results: A smaller number of patients requiring at least 7 continuous days of inotropic therapy through 24 weeks indicates an improvement in the LCZ696 arm versus Valsartan.

### **11.8 – Tertiary Endpoint #8**

Endpoint Description: Number of subjects listed for transplant (1A, 1B or 1-4), transplanted or implanted with an LVAD through 24 weeks, using the pre-COVID-19 population.

Response Variable Definition: Number of patients listed for heart transplant, transplanted or implanted with a LVAD between Randomization and Week 24.

Additional Covariates in Addition to Randomized Treatment: atrial fibrillation status at time of randomization

Handling of Dropouts and Missing Data: Each patient will be evaluated based on the available follow-up. No adjustment for incomplete follow-up will be made.

Sensitivity Analysis: Re-calculate the endpoint analysis using the original ITT population.

Statistical Tests: A logistic regression model (PROC LOGISTIC in SAS) will be used to estimate and statistically compare whether there is differential rate of subjects meeting the endpoint between the treatments.

Interpretation of Results: A smaller number of patients requiring LVAD or heart transplant, including listing for transplant, through 24 weeks indicates an improvement in the LCZ696 arm versus Valsartan.

### **11.9 – Tertiary Endpoint #9**

Endpoint Description: Change in eGFR levels compared to baseline. Renal function was assessed at baseline, weeks 2, 4, 8, 12, and 24, using the pre-COVID-19 population.

Response Variable Definition: Change from baseline in eGFR at Weeks, 2, 4, 8, 12, and 24.

Additional Covariates in Addition to Randomized Treatment: atrial fibrillation status at time of randomization

Handling of Dropouts and Missing Data: No adjustment for missing data will be made.

Sensitivity Analysis: Re-calculate the endpoint analysis using the original ITT population.

Statistical Tests: A mixed model (PROC MIXED in SAS) will be used to estimate and statistically compare changes in GFR between Baseline and Weeks 2, 4, 8, 12 and 24 values.

Interpretation of Results: A higher GFR indicates better renal function in the LCZ696 arm vs Valsartan.

### **11.10 – Tertiary Endpoint #10**

Endpoint Description: Change in cystatin C levels compared to baseline. Renal function was assessed at baseline, weeks 2, 4, 8, 12, and 24, using the pre-COVID-19 population.

Response Variable Definition: Change from baseline in Cystatin C at Weeks, 2, 4, 8, 12, and 24.

Additional Covariates in Addition to Randomized Treatment: atrial fibrillation status at time of randomization

Handling of Dropouts and Missing Data: No adjustment for missing data will be made.

Sensitivity Analysis: Re-calculate the endpoint analysis using the original ITT population.

Statistical Tests: A mixed model (PROC MIXED in SAS) will be used to estimate and statistically compare changes in Cystatin C between Baseline and Weeks 2, 4, 8, 12 and 24 values.

Interpretation of Results: A lower cystatin C indicates improvement in the LCZ696 arm vs Valsartan.

### **11.11 – Tertiary Endpoint #11**

Endpoint Description: Number of subjects with unanticipated use of IV diuretics (outpatient, ER or inpatient) through 24 weeks, using the pre-COVID-19 population.

Response Variable Definition: An indicator for patient having unanticipated use of IV diuretics (outpatient, ER or inpatient) through 24 weeks.

Additional Covariates in Addition to Randomized Treatment: atrial fibrillation status at time of randomization

Handling of Dropouts and Missing Data: Each patient will be evaluated based on the available follow-up. No adjustment for incomplete follow-up will be made.

Sensitivity Analysis: Re-calculate the endpoint analysis using the original ITT population.

Statistical Tests: A logistic regression model (PROC LOGISTIC in SAS) will be used to estimate and statistically compare whether there is differential rate of subjects meeting the endpoint between the treatments.

Interpretation of Results: A smaller number of patients requiring unanticipated use of IV diuretics through 24 weeks indicates an improvement in the LCZ696 arm versus Valsartan.

## 11.12 – Tertiary Endpoint #12

Endpoint Description: Change in AUC in the Kansas City Cardiomyopathy Questionnaire (KCCQ) compared to baseline – both for overall and clinical summary scores, using the pre-COVID-19 population.

Response Variable Definition: The KCCQ questionnaire was completed at Screening (considered Baseline for this analysis), Week 4, Week 12 and Week 24. The endpoint will be derived in a similar fashion to the primary endpoint (see 9.1).

Additional Covariates in Addition to Randomized Treatment: atrial fibrillation status at time of randomization, appropriate baseline value of each KCCQ score

Handling of Dropouts and Missing Data: If missing KCCQ score at Week 24, use last observation carried forward (LOCF) from previous post-Baseline time point with available KCCQ score data. No adjustment will be made for missing Baseline results.

Sensitivity Analysis: Re-calculate the endpoint analysis using the original ITT population.

Statistical Tests: A general linear model (PROC GLM in SAS) will be used to test the significance of differences in the area under the curve for the each KCCQ score between the two treatment arms.

Interpretation of Results: A higher KCCQ score indicates an improved KCCQ score in the LCZ696 arm versus Valsartan.

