## 9. Endpoint Descriptions

### 9.1 – Primary Endpoint

**Endpoint Description:** The log of the proportional change from baseline in the area under the curve for the ratio of NT Pro BNP compared to baseline, using the pre-COVID-19 population.

**Response Variable Definition:** All available time points will be used in the calculations. NT Pro BNP is measured at Baseline, Week 2, Week 4, Week 8, Week 12 and Week 24. The ratio of each of the post-Baseline measures will be calculated versus Baseline. The area under the entire piecewise dataset is the response variable. A visual example is provided showing a patients' hypothetical data for NT Pro BNP ratio to Baseline.

This area is determined by calculating the sum of the areas of each of the individual trapezoids. Each trapezoidal area is composed of the area bordered by the time interval on the x-axis (e.g., 0 to 2 Weeks), the respective NT Pro BNP ratio at each of the time points on the y-axis (e.g., 1 at x=0 and 0.7 at x=2), and the line segment connecting the NT Pro BNP ratios between the two y-axis values (1 and 0.7). The number of trapezoids available will depend on the completeness of the data.

It is expected that NT Pro BNP measurements may not be measured exactly at the specified time points. For example, the measurement corresponding to the 12 Week time point may actually be measured for example at 11 or 12.5 Weeks after randomization. In calculating the AUC, the measurement corresponding to Baseline will always be set at the 0 time point. Each post-Baseline visit will use the value for the visit timing, even if that timing is not exact (e.g., Week 12 visit will always assign a 12 for the x-axis). The final step in the calculation is to take log of the calculated area under the curve.

Additional Covariates in Addition to Randomized Treatment: Baseline log NT Pro BNP, atrial fibrillation status, random effect of patient

Handling of Dropouts and Missing Data: If missing NT Pro BNP at Week 24, use last observation carried forward (LOCF) from previous post-Baseline time point with available NT Pro BNP data. No adjustment will be made for missing Baseline results.

Sensitivity Analysis: Several sensitivity analyses will be performed.

- 1) Complete cases, using patients with available Baseline and Week 24 Week 24 NT Pro BNP data
- 2) For patients missing Week 24 value, impute 2.5xBaseline value for Week 24

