### 11.13 – Tertiary Endpoint #13

**[Tertiary Endpoint #13 will only be assessed on the first 200 patients randomized, as generated for the Interim Analysis. A decision was made by the Executive Committee to not assay for BNP at trial completion for the remaining randomized patients.]**

Endpoint Description: The log of the proportional change from baseline in the area under the curve for the ratio of NT Pro BNP/BNP compared to baseline.

Response Variable Definition: The was collected at Baseline, Week 2, Week 4, Week 8, Week 12 and Week 24. The endpoint will be derived in a similar fashion to the primary endpoint (see 9.1).

Additional Covariates in Addition to Randomized Treatment: atrial fibrillation status at time of randomization, baseline value of log(BNP) and log(NT Pro BNP).

Handling of Dropouts and Missing Data: If missing biomarker data at Week 24, use last observation carried forward (LOCF) from previous post-Baseline time point with available data. No adjustment will be made for missing Baseline results.

Sensitivity Analysis: No sensitivity analyses will be performed.

Statistical Tests: A general linear model (PROC GLM in SAS) will be used to test the significance of differences in the area under the curve for the ratio of NT Pro BNP to BNP between the two treatment arms.

Interpretation of Results: A lower value for the NT Pro BNP/BNP ratio indicates an improvement in the LCZ696 arm versus Valsartan.

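### No KCCQ analysis in SAP 11.12 reflects death, and the section does not say whether the KCCQ AUC is a change score or a log ratio to baseline

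*SAP*

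**What the plan says.** SAP 11.12 defines the endpoint as "Change in AUC in the Kansas City Cardiomyopathy Questionnaire (KCCQ) compared to baseline", for the overall and clinical summary scores. On timing it says "The KCCQ questionnaire was completed at Screening (considered Baseline for this analysis), Week 4, Week 12 and Week 24". The derivation is given only by cross-reference: "The endpoint will be derived in a similar fashion to the primary endpoint (see 9.1").

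SAP 9.1, the section referred to, has two steps that matter here. First, "The ratio of each of the post-Baseline measures will be calculated versus Baseline"; the trapezoids are then summed. Second, "The final step in the calculation is to take log of the calculated area under the curve".

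For missing data, 11.12 states "If missing KCCQ score at Week 24, use last observation carried forward (LOCF) from previous post-Baseline time point with available KCCQ score data". Death is not mentioned. The model is a general linear model with atrial fibrillation status and the untransformed baseline KCCQ score as covariates. The single sensitivity analysis repeats the same calculation in the original ITT population.

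Two neighbouring sections are handled differently:
- **SAP 9.1, Sensitivity Analysis 6:** a Wilcoxon test for NT-proBNP that gives deaths the worst ranks, ordered by time to death.
- **SAP 11.13:** uses the same cross-reference to 9.1 but states its scale outright, "The log of the proportional change from baseline in the area under the curve for the ratio of NT Pro BNP/BNP", and adjusts for logged baselines.

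**The concern.** **Death.** Patients in this trial have advanced heart failure, and a missing Week 24 questionnaire will sometimes mean that the patient has died. Carrying the last score forward treats that patient as someone whose health status stayed the same. If one arm had fewer deaths, or more, the KCCQ comparison would not show it, in the main analysis or in the sensitivity analysis. The protocol (16.2 and 16.4) already treats missing NT-proBNP as informative. It names deaths among the reasons that 20-25% of subjects may lack a Week 24 value, and it plans a worst-rank check for that marker. KCCQ is due from the same patients at the same visit and has no such check. The same rule also serves a quite different cause of missingness. SAP Section 3 removes some visit data for 25 of the 335 patients because of the pandemic cut-off, and wherever that takes out the Week 24 KCCQ it is filled in the same way as after a death.

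**Scale.** A programmer could produce a log-ratio analysis or a change-score analysis and claim that either follows 11.12. The two weight patients differently, so the choice should not be left until the data are in hand.

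**Working it through.** The documents give no power, SD, effect size or baseline distribution for KCCQ, so there is no planned figure to reproduce. The check applies the 9.1 trapezoid rule to the KCCQ visit times.

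**1. Weight of each visit.** Visits are at 0, 4, 12 and 24 weeks. Each visit's weight is half the sum of the intervals next to it:
- Week 0: 4/2 = 2
- Week 4: (4 + 8)/2 = 6
- Week 12: (8 + 12)/2 = 10
- Week 24: 12/2 = 6
- Total: 24

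**2. What carrying forward fills in.**

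| Last score before death | Weeks held at that score | Weight on unobserved visits |
|---|---|---|
| Week 4 | 20 of 24 | (10 + 6)/24 = 67% |
| Week 12 | 12 of 24 | 6/24 = 25% |
| Baseline only | no post-baseline score to carry | no AUC; presumably excluded |

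The written rule fills only Week 24. When Week 12 is also missing, the single trapezoid from Week 4 to Week 24 joins two equal values, so the area is the same as if Week 12 had been filled too.

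**3. One patient.** Take an illustrative baseline of 40 and a score of 40 at every visit until death. On the ratio scale the carried-forward AUC is 1 × 24 = 24.0, identical to that of a stable survivor. If visits after death scored 0, the AUC would be 2 + 6 = 8.0 (last seen at Week 4) or 2 + 6 + 10 = 18.0 (last seen at Week 12).

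**4. Between arms.** Assume death times spread evenly over 24 weeks, a mean score of 40 and no difference between arms among the living. With zero scoring after death, the average share of the AUC lost per death is
(4/24)(22/24) + (8/24)(16/24) + (12/24)(6/24) = (88 + 128 + 72)/576 = 0.50.
Mortality of 20% v 10% then moves the time-averaged score by 0.10 × 0.50 × 40 = 2.0 points, and 10% v 5% by 0.05 × 0.50 × 40 = 1.0 point. A simulation on these lines (baseline SD 20) gave 2.05 and 1.05 points with zero scoring, and 0.01 and 0.06 with the planned rule. Zero is only one way to score death. The comparison shows that the planned rule does not respond to a mortality difference.

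**5. Scale.** Take a gain of 10 points at Weeks 4, 12 and 24 from baseline b. The ratio AUC is 24 + (10/b)(6 + 10 + 6) = 24 + 220/b. The 9.1 response is the log of this. Subtracting log 24, a constant that does not affect the treatment comparison, gives:

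| Baseline (illustrative) | Ratio AUC | log(AUC/24) | Change AUC (point-weeks) |
|---|---|---|---|
| 10 | 46.0 | 0.65 | 220 |
| 60 | 27.67 | 0.14 | 220 |

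The same gain therefore counts about 4.6 times as much (0.651/0.142) at baseline 10 as at baseline 60 on the log-ratio scale, and equally on the change scale. The ratio is undefined at a baseline of 0, and no rule covers that case.

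**6. Raw AUC or change AUC.** The AUC of score minus baseline equals the AUC of the score minus 24 × baseline. With baseline in the linear model, the two give the same treatment estimate. The open question is therefore only whether a ratio and log are taken.

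**The case against.** The strongest reply is that whether death belongs inside a health-status endpoint is a choice of estimand, and that the plan counts death elsewhere: in the days-alive endpoint (SAP 10.1), in time to death and the death composites (SAP 11.1, 11.2, 11.4 and 11.5), and as the top tier of the win ratio (SAP 12.1). Protocol 16.4 specifies worst ranks for NT-proBNP only, and 16.5 calls for general linear models for continuous endpoints, which 11.12 follows. This stands in part: nothing promised is missing, and the main KCCQ analysis need not penalise death. But none of those other analyses uses KCCQ, so they do not show whether the KCCQ result holds once deaths are counted.

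Three stronger readings are tempting, and the documents do not support them.
- **That the KCCQ analysis is driven by a few patients with very low baselines.** This needs the log-ratio reading and a known baseline distribution. The first is not settled and the second is not given. Nor does the protocol's wording decide the scale: Protocol 13.3 speaks of a change in AUC for both KCCQ and the NT-proBNP/BNP ratio, and the SAP implements the latter as a log proportional change.
- **That every patient who dies keeps a last living score.** The rule draws only on post-baseline scores, so deaths before Week 4 leave no value.
- **That 83% or 50% of the AUC is imputed.** Those are shares of elapsed time (20/24 and 12/24). The weight on unobserved visits is 67% or 25%.

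**Conclusion.** The point holds in two parts.

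The first rests on explicit text. The KCCQ rule does not separate death from other missing data, and no KCCQ analysis reflects death. For patients who die after giving a post-baseline score, visits carrying 67% or 25% of the weight are filled with the last living score. Earlier deaths have no value, and the section does not say what happens to them; exclusion is the natural inference. The 1 to 2 point between-arm figures rest on assumed mortality, an assumed mean score of 40, even timing of deaths and zero scoring. They are illustrations, not forecasts.

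The second is an ambiguity, not an established error. The cross-reference read literally gives a log ratio. The section's own change wording, its untransformed baseline covariate and the contrast with SAP 11.13 point to a change score. The 0.65 v 0.14 contrast applies only under the literal reading and at the illustrative baselines.

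This is a tertiary endpoint. The primary conclusion is unaffected, and the change is desirable rather than essential.

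**What to change.** 1. **Add one KCCQ sensitivity analysis to SAP 11.12.** Use a Wilcoxon test in which patients who die before the Week 24 visit take the worst ranks in order of time to death, and the others are ranked by their KCCQ AUC. This reuses Sensitivity Analysis 6 of the primary, with survivors ranked in the opposite direction because a higher KCCQ is better. It also brings back patients who die before Week 4.
2. **State the scale in 11.12.** The response is the AUC of score minus baseline on the original scale, with no ratio and no log, adjusted for baseline score as already planned. This also removes the problem of a zero baseline.
3. **State in the missing-data rule that death is distinct from other missingness,** and what happens to a patient with no post-baseline score.

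The cost is a few lines of SAP text and one extra analysis from existing code. The drawback is that a worst-rank result mixes survival with health status and gives no effect in KCCQ points, so it should remain a sensitivity analysis beside the planned model.
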